- An occurrence of an episode of atrial fibrillation lasting greater than 30 seconds and documented on either 12 lead ECG or on ambulatory ECG monitoring in the 12 months following an ablation procedure
- Time in days from ablation procedure to the occurrence of an episode of atrial fibrillation lasting greater than 30 seconds and documented on either 12 lead ECG or on ambulatory ECG monitoring
- An occurrence of an episode of atrial fibrillation lasting less than 30 seconds and documented on either 12 lead ECG or on ambulatory ECG monitoring in the 12 months following an ablation procedure
- Recurrence of the ablated arrhythmia
- Occurrence of a novel arrhythmia other than atrial fibrillation
- Discontinuation of Anticoagulation
- Stroke
- Myocardial Infarction
- Hospitalisation for heart failure
- Hospitalisation for bleeding episode
- Hospitalisation for any cause
- CV Death
- Death from any cause
- Change in quality of life questionnaire

Subject Identification and Recruitment

Subject Groups

The study is organised with subjects divided into specific groups which will be analysed separately. These groups include;

- 1. Paroxysmal Atrial Fibrillation Group
- 2. Supraventricular Tachycardia (SVT) Ablation Group
- 3. Atrial Flutter Ablation Group
- 4. Pulmonary Vein Isolation Group

The participant's past history of abnormal heart rhythms will be used to indicate their risk for developing atrial fibrillation based on previous epidemiological studies. Those with known clinical paroxysmal atrial fibrillation will represent the highest risk group, those undergoing ablation for an SVT will be considered low risk and those undergoing ablation for atrial flutter will form an intermediate risk group.

Potential participants will be identified as being possible study candidates at the time of clinical review as part of their usual care. Clinicians or other healthcare professionals performing such a clinical review will identify the subject as a potential candidate for recruitment, will mention the study to the potential participant and highlight their case to the study team for so that they may approach that person to recruit them. For participants in Part B, it is anticipated that this will be the review from which they are listed for an ablation procedure. The clinical team will also review the case notes for patients already listed for an ablation procedure in their centre and potential candidates identified in this manner will be approached.

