- Participants must have a pattern of symptoms and investigation results consistent with a diagnosis of paroxysmal atrial fibrillation

Group 2 – SVT Ablation Group

- Participants must have a history of arrhythmia with documented regular, narrow complex tachycardia available on either 12 lead ECG or ambulatory ECG monitor recording
- Participants must be listed to undergo an Electrophysiology study with a view to performing an ablation procedure
- Participants must go on to have an ablation procedure for either Atrio-Ventricular Re-entrant Tachycardia (AVRT) or Atrio-Ventricular Nodal Re-entrant Tachycardia (AVNRT) with a defined procedural endpoint

Group 3 – Atrial Flutter Ablation Group

- Participants must have a history of arrhythmia with 12 lead ECG documentation fulfilling prespecified criteria for diagnosis of common type (cavotricuspid isthmus dependent) atrial flutter
- Participants must be listed to undergo a cavotricuspid isthmus ablation for common type atrial flutter
- Participants must go on to have only a cavotricuspid isthmus ablation for common type atrial flutter
- Sustained bi-directional cavotricuspid isthmus block must have been demonstrated as the endpoint for the ablation procedure

Group 4 – Pulmonary Vein Isolation Group

- Participants must have a history of arrhythmia with 12 lead ECG or ambulatory ECG monitoring recordings documenting a diagnosis of atrial fibrillation
- Participants must be listed to undergo an ablation procedure for atrial fibrillation with the intent of the attending physician to perform pulmonary vein isolation alone as an ablation strategy
- Participants must be in sinus rhythm at the time that they enter the Cardiac Electrophysiology Laboratory for their ablation procedure.
- Participants must have an ablation procedure for atrial fibrillation and this must have involved only ablation to achieve pulmonary vein isolation
- Pulmonary vein isolation must have been demonstrated as the endpoint for the ablation procedure

Exclusion Criteria

All Participants in All Groups

- Allergy to Isoprenaline
- Any treatment with Amiodarone in the 3 months prior to ablation procedure
- Hypertrophic cardiomyopathy
- Suspected acute myocarditis
- Uncorrected, severe valvulopathy graded by transthoracic echocardiographic parameters
- An Acute Coronary Syndrome within the last 6 months
- Recent (within the last 6 months) or scheduled coronary revascularisation

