- Ongoing angina symptoms without investigations demonstrating the absence of myocardial ischaemia
- Left ventricular ejection fraction measured at <30%
- Symptoms of decompensated heart failure syndrome in the last 3 months
- Severe obstructive lung disease
- Pregnancy at the time of enrolment or a desire to become pregnant during the study period
- Women who are breastfeeding
- Reduced life expectancy not associated with cardiovascular disease (less than 1 year)
- Unable to provide informed consent

Group 1 – Paroxysmal Atrial Fibrillation Group

- Any past history of episode of persistent atrial fibrillation at the time of enrolment to the study
- Treatment with any antiarrhythmic agent within six half-lives of that agent from before an administration of the study drug infusion

Group 2 – SVT Ablation Group

- Any past history of atrial fibrillation documented on 12 lead ECG or ambulatory ECG monitor
- Any past history of atrial flutter documented on 12 lead ECG or ambulatory ECG monitor
- Characterisation of SVT as any arrhythmia other than ANRT or AVNRT
- Treatment with any antiarrhythmic agent within six half-lives of that agent from the ablation procedure (including intra-procedural use) with the exception of isoprenaline and adenosine

Group 3 – Atrial Flutter Ablation Group

- Characterisation of arrhythmia as any arrhythmia other than cavo-tricuspid isthmus dependent atrial flutter at the time of ablation
- Treatment with any antiarrhythmic agent within six half-lives of that agent from the ablation procedure (including intra-procedural use) with the exception of isoprenaline and adenosine

Group 4 – Pulmonary Vein Isolation Group

- Requirement for a more extensive ablation strategy than pulmonary vein isolation alone
- Intra-procedural treatment with any antiarrhythmic agent with the exception of isoprenaline and adenosine
- Treatment with any antiarrhythmic agent in the days before the ablation within six half-lives of that agent from the ablation procedure

Participant Information

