It is noted that previous literature suggests that the proportion of patients with a past history of atrial fibrillation who are inducible with isoprenaline is greater than 80%. This does not fit with our interpretation of day to day clinical practice and hence the study is powered to detect a far lower arte of inducibility. We will however perform a pre-specified interim analysis of the Pulmonary Vein Isolation Group once 10 participants with a past history of atrial fibrillation have been randomised to each arm of the study (Experiment 2). If a significant result is detected, enrolment to that block will be discontinued.

Statistical analysis

The analysis of the disagreement between repeated isoprenaline infusions in terms of ability to induce atrial fibrillation will estimate the proportion of disagreement with a 1-sided 95%CI for the proportion. A 2-sided 90%CI is first calculated and the upper limit of this interval gives the required upper limit of a 1-sided 95%CI. If the estimated upper limit is < 20% (the chosen cut-off for clinically significant disagreement) then agreement between repeated infusions will be considered acceptable.

The randomised comparison of proportion of patients inducible between placebo and isoprenaline will use the chi-squared test or the Fisher's exact test if numbers of patients in some categories are small.

It is anticipated that the rate of induced episodes of arrhythmia in a number of the groups where they are being given placebo infusion will approach zero. If the results of the study demonstrate that the rate of inducibility in the SVT group or atrial flutter group being given placebo infusion is zero, we would consider it acceptable to use one sided tests of significance.

Study Duration

We aim to recruit 235 participants over a 24 month recruitment period. It is anticipated that the majority of subjects will be recruited from the Bournemouth site.

- Start Date: 01/09/2014
- Estimated Date of End of Trial: 01/09/2017
- Maximum Duration of Participation: 12 months

Study Procedure

The study will require a minimum of 2 encounters with the study team. For subjects in the group of participants requiring the most visits, the study schedule requires 7 visits over 12 months. Usual care for this group would involve 4 visits to hospital, one of these is not required by the study participants and 3 are combined with study visits.

Infusion Protocol

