Participants will be monitored for at least 30 minutes after the end of the infusion protocol. At this point they will have their basic physiological observations repeated to include pulse rate and rhythm, blood pressure and oxygen saturations. Release from hospital will be at the discretion of the supervising clinician. It is anticipated that a small number of subjects will be required to remain under observation for a number of hours especially in the context of the need for sedation and cardioversion for subjects who remain in persistent arrhythmia following the infusion.

At release from this visit, subjects will be advised to restart any antiarrhythmic agents which they had withheld as part of the study protocol for this visit. They will also be provided with contact information for the study team and advised that they should contact the team with any concerns or problems following their participation in the project. The conclusion of this visit represents the end of their participation in the study.

Study Procedure - Protocol Part B

This part of the protocol involves participants who will have been recruited as they are undergoing an ablation procedure on the NHS. The SVT ablation, atrial flutter ablation and the pulmonary vein isolation groups will be recruited to this part of the study.

The study infusion will be delivered in a double blinded, randomised manner. Each participant group will undergo 1 to 1 randomisation to receive either an isoprenaline infusion at the start and end of their ablation or the placebo infusion at the start and end.

Part B of the protocol will require a minimum of 4 encounters with the study team. For subjects who have given consent to undergo additional ECG monitoring, the study schedule requires 7 visits over the 12 months. Usual NHS care for all participants enrolled to Part B of the protocol would involve 4 visits to hospital, one of these may not be required by the study participants and 3 are combined with study visits.

Schedule for participants involved in Protocol Part B								
Study Procedure	NHS clinical review and / or subsequent telephone conversation	Visit 1 (Enrolment)	Visit 2 (Ablation Procedure)	Visit 3 (6 week F/U)	Visit 4 (3 month F/U)			
Identification of possible suitable subject	x							
Subject given written information and approached about study	x							
Eligibility assessment		х						
Informed Consent		х						
Demographic data collection		х						
Medical history data collection		х						

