The investigators are authorised to provide alternative treatment to that specified in the protocol at any stage if he/she feels it is in the participant's best interest. The reasons for deviation from protocol should be recorded.

Reasons for Discontinuation of Subject's Participation in Study

A subject can voluntarily discontinue their involvement in the study at any stage without the need to give reason and without prejudicing further treatment. In addition, subjects will be removed from the study if they cease to meet the inclusion criteria after enrolment (eg participant in SVT block has electrophysiology study that demonstrates atrial tachycardia rather than ANRT or AVNRT) or if they develop one of the exclusion criteria (eg require treatment with amiodarone in the time between the 2 infusions required for Protocol Part A). Subjects will also be excluded from continuation in the study if they develop anaphylaxis, chest pain or ECG features of myocardial ischaemia during the infusion protocol.

Where subjects withdraw or are excluded from the study after enrolment but prior to their completion of the study schedule, a further subject will be recruited to their subject group to take their place. Any data collected before withdrawal may be included in the study results.

End of Study Actions

Having withdrawn from the study, been excluded from continued participation or having completed their final visit or ambulatory ECG recording, participants will have completed their involvement in the study. There are no specific interventions required at completion of the study schedule. All participants will be informed that they may still contact the study team should they have questions or concerns regarding their health or their involvement in the study.

Safety Assessment

Adverse Events

Definitions

- Adverse Event (AE): any untoward medical occurrence in a patient or clinical study subject.
- Serious Adverse Event (SAE): any untoward and unexpected medical occurrence or affect that:
 - Results in death
 - Is life-threatening refers to an event in which the subject was at risk of death at the time of the event; it does not refer to an event which hypothetically might have caused death if it were more severe
 - Requires hospitalisation, or prolongation of existing inpatients' hospitalisation
 - Results in persistent or significant disability or incapacity
 - o Is a congenital anomaly or birth defect

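### In Part B, removal and replacement run to the end of follow-up rather than to the last infusion, so people with complete infusion outcomes are replaced by newly infused ones and follow-up stops after certain endpoint events

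*Protocol*

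**What the plan says.** Protocol, Reasons for Discontinuation of Subject's Participation in Study: subjects are removed if they stop meeting the inclusion criteria "or if they develop one of the exclusion criteria". Someone who withdraws or is excluded after enrolment and "prior to their completion of the study schedule, a further subject will be recruited to their subject group to take their place". Data gathered before withdrawal *may* enter the results; no rule says when. End of Study Actions treats a person excluded from continued participation as having finished their involvement.

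Protocol, Study Procedure - Protocol Part B: the infusion is given at the start and end of the ablation, at Visit 2. Participation then ends at the 3-month visit, except that with additional ECG monitoring "the study schedule requires 7 visits over the 12 months".

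Protocol, Exclusion Criteria for all groups: the list includes "An Acute Coronary Syndrome within the last 6 months" and "Symptoms of decompensated heart failure syndrome in the last 3 months", neither tied to enrolment or to the procedure.

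Protocol, Observational Endpoints: the list includes myocardial infarction and "Hospitalisation for heart failure".

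Protocol, Study Duration: "We aim to recruit 235 participants over a 24 month recruitment period".

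**The concern.** Replacement is normally used to make good a missing outcome. Here the trigger is an unfinished schedule, and in Part B the schedule outlasts the infusion outcomes by months. A participant with both infusions recorded who withdraws in month 2, or in month 9 if monitored, would be replaced by someone who is randomised and infused although nothing is missing from Experiments 2 to 6. The protocol's section on benefits expects no direct benefit from isoprenaline, so this exposure has no return. The number infused would also depend on what happens in follow-up.

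The removal rule adds a second problem. Two of the all-group exclusion criteria overlap with events that the follow-up is meant to count. A participant who has such an event would leave the scheduled follow-up at that point, when later atrial fibrillation, stroke or death is still of interest.

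**Working it through.** **1. When the outcome is complete and when the schedule ends**

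| | Infusion endpoints complete | Schedule ends |
|---|---|---|
| Part A (Experiment 1) | Second infusion visit | Same visit |
| Part B, no extra monitoring | Visit 2 (ablation day) | 3 months |
| Part B, extra monitoring | Visit 2 (ablation day) | 12 months |

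The safety endpoints for each infusion close 24 hours after it starts. The gap between the two columns exists only in Part B.

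**2. The plan's own figures**

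- Total: 35 (Part A) + 2 × 30 (pulmonary vein isolation) + 2 × 35 (flutter) + 2 × 35 (SVT) = 35 + 60 + 70 + 70 = 235. This matches Study Duration exactly, so the total holds no reserve for replacements. Part B is 60 + 70 + 70 = 200.
- Per arm, 30% against 1%, two-sided 5%, 90% power, no continuity correction: n = [1.960 × √(2 × 0.155 × 0.845) + 1.282 × √(0.30 × 0.70 + 0.01 × 0.99)]² / 0.29² = 30.6, so 31. This matches Sample Size Calculation.

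**3. Extra people infused under the rule as written**

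Let d be the share of Part B participants who withdraw or are excluded after Visit 2 and before the end of their schedule. The protocol gives no value, so d is assumed. A replacement can also leave and be replaced, so the number infused is 200 / (1 − d), rounded up.

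| d (assumed) | Infused in Part B | Extra people | Extra infusions, at most |
|---|---|---|---|
| 2% | 205 | 5 | 10 |
| 5% | 211 | 11 | 22 |
| 10% | 223 | 23 | 46 |
| 20% | 250 | 50 | 100 |

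With 1:1 allocation about half of the extra people would receive isoprenaline. The last column is a ceiling, because the pre-ablation infusion is omitted for anyone already in persistent arrhythmia. If replacement were limited to a missing infusion outcome or ineligibility found by the last infusion, these departures would cause no extra infusions.

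**4. Effect on power**

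For 30% against 1%, power is 89.4% at 30 per arm, 90.4% at 31 and 92.9% at 34. Extra participants raise it slightly.

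**5. Overlap of exclusion criteria and endpoints**

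- A follow-up myocardial infarction is an observational endpoint and would meet the acute coronary syndrome exclusion.
- A heart failure admission is an observational endpoint and would ordinarily meet the decompensated heart failure exclusion.

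In both cases the event comes before the removal, so it can be recorded. What is lost is the scheduled observation afterwards.

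**The case against.** The best defence is intent. Both examples given with the removal rule arise before the outcome is complete: a wrong mechanism found at the electrophysiology study, and amiodarone between the two Part A infusions. Several exclusion criteria are tied to enrolment, ablation or infusion, which suggests that the list screens fitness for the infusion. A narrower rule was probably meant. This stands as an account of intent, but the operative sentences contain no such limit.

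It also stands that the follow-up endpoints are described as descriptive and without power, and come from an optional subset. No primary result is shown to change.

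A reader might infer more than the document supports:

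- *That a missed visit triggers replacement.* The rule applies to withdrawal or exclusion. Missing a contact is neither, and the 3-month interview may be by telephone.
- *That the calendar makes the rule impossible.* The end date of 01/09/2017 is an estimate and 24 months of recruitment is an aim. A replacement without additional monitoring finishes at 3 months.
- *That the event rates are biased low.* Earlier data may be used, adverse events go on the case report form, and serious ones are followed until resolved or until a decision to stop. The triggering event need not be lost.

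**Conclusion.** The point holds for Part B as a defect in a stated rule. Followed literally, it exposes people to study infusions that Experiments 2 to 6 do not need: about 11 to 50 people if 5% to 20% of the 200 Part B participants withdraw or are excluded after Visit 2. That range is assumed, and at 2% the figure is 5. The rule also cuts off scheduled follow-up after an acute coronary syndrome or decompensated heart failure. Because use of earlier data is discretionary, it leaves open whether the person who left, the replacement or both are analysed.

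Part A is unaffected, since its schedule ends with its second infusion, and power is not harmed. The matter should be corrected because the exposure is avoidable and the change is small. It does not put the primary conclusions in doubt.

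**What to change.** Amend the discontinuation section of the protocol in four places:

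1. Limit removal for lost eligibility, or for a newly met exclusion criterion, to the period up to the last study infusion.
2. Replace only participants removed as ineligible in that period, or whose required infusion outcome is missing. The first limb matters: a pulmonary vein isolation participant found during the procedure to need more extensive ablation may already have a pre-ablation outcome, and must stay replaceable.
3. State that infusion outcomes already recorded from people who leave afterwards *will* be analysed, in place of *may*.
4. Continue scheduled follow-up after an endpoint event unless consent is withdrawn.

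The separate rule on anaphylaxis, chest pain or ischaemic ECG features during an infusion is not part of this point. The cost is a few sentences in an amendment and slightly fewer complete records in the descriptive follow-up set.

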All parts of this investigation utilise a standard infusion protocol of a study drug. This study drug will be isoprenaline or placebo delivered in a double blinded fashion or will be open label isoprenaline dependent on which experiment it is being administered for. In all cases the infusion protocol will be identical as will the associated outcomes recorded. Although different experiments within the protocol call for different, statistically driven endpoints, the endpoints for every administration of a study drug infusion protocol are the same.

Outcome after which infusion would be stopped

- Occurrence of atrial fibrillation lasting greater than 30 seconds during study drug infusion protocol
- Occurrence of an arrhythmia other than atrial fibrillation, sinus tachycardia or junctional rhythm lasting greater than 30 seconds during study drug infusion protocol
- Discontinuation of the study drug infusion
 - o Severe tremulousness or anxiety
 - Complaints of severe chest tightness
 - Decrease in systolic blood pressure to consistently < 70mmHg
 - Electrocardiographic changes suggestive of myocardial ischaemia

Pre-specified outcomes to be recorded but which would not trigger cessation of infusion

- Occurrence of atrial fibrillation lasting less than 30 seconds during study drug infusion protocol
- Occurrence of an arrhythmia other than atrial fibrillation, sinus tachycardia or junctional rhythm lasting less than 30 seconds during study drug infusion protocol
- Time from start of infusion protocol to occurrence of atrial fibrillation
- Rate of infusion at time of occurrence of atrial fibrillation
- Maximum tolerated rate of study drug infusion prior to its cessation for any reason

Safety Endpoints associated with each infusion administration

- Death within 24 hours of start of study drug infusion protocol
- Stroke within 24 hours of start of study drug infusion protocol
- Myocardial Infarction within 24 hours of start of study drug infusion protocol

Observational Data

Collected from Additional Monitoring Group

Participants from some groups recruited will be offered the chance to have some additional follow up monitoring after their ablation procedure. This data will be purely descriptive and unpowered. It will be analysed looking at the following endpoints.

Observational Endpoints

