The study participants will all undergo measurement of physiological observations including pulse rate, blood pressure and oxygen saturation levels as well as a 12 lead ECG recording on arrival on the day of their ablation procedure. All subjects will have been asked to stop antiarrhythmic drugs 6 half-lives prior to this visit and have been asked to starve for 6 hours prior to their visit. These would all be considered part of their usual care in that setting.

Once the subject has entered the cardiac electrophysiology laboratory they will have monitoring and specialist electrophysiology equipment attached as is usual prior to an ablation procedure. A dedicated defibrillation device will be available. The operator will then gain intravenous access via the femoral vein as is standard practice and insert the required number of venous sheaths. Where

Usual NHS Care around an ablation procedure							
Procedure	NHS clinical review	Ablation	6 week visit	Extra Visit not in study	3 month F/U		
NHS Clinical Review in Outpatient Department	×				x		
Observations (to include pulse, BP, SpO ₂ , Weight)		x					
12 lead ECG	x	x			x		
Novacor fitting (7 day ECG monitor)			x				
Novacor return (7 day ECG monitor)				×			
Ablation Procedure		х					
Consultation time	20 mins	30 mins	N/A	N/A	20 mins		
Intervention time	20 mins	120 mins	20 mins	10 mins	N/A		

the optional consent is provided, blood samples may be taken via the sheaths that are sited.

Before catheters are inserted into the heart, the patient will be sedated so that they are asleep but responsive to voice. The level of sedation will be recorded along with the total dose at this point. The operator will then attach the study infusion to the side arm of one of the femoral sheaths. Heart rate and blood pressure will be recorded at this point and at one minute intervals from this point until the end of the study drug infusion. The pre-ablation

study drug infusion will then be started and administered as per the drug infusion protocol already described.

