If arrhythmia persists for greater than 10 minutes, it will be at the discretion of the attending clinician to decide whether to perform DC cardioversion, continue to wait or to proceed with the intended ablation procedure. If the participant is in persistent arrhythmia at the time of the start of the preablation infusion (most likely to occur in the atrial flutter ablation group) then that infusion will not be performed and the operator will proceed to the ablation procedure. Such participants will receive the post-ablation infusion as per protocol.

After the pre-ablation study drug infusion, the attending clinician will then proceed to the clinically indicated ablation procedure. The diagnosis and endpoint for the ablation procedure will be
recorded. When the attending physician is confident they have achieved their endpoint for the procedure, efforts will be made to induce a similar level of sedation as that recorded at the time of the pre-ablation study drug infusion. It is accepted that this may not be possible in the real world setting.

Once efforts have been made to achieve a similar level of sedation, the post-ablation study drug infusion will be administered using the standard infusion protocol for the identical infusion delivered prior to ablation.

All patients will be expected to leave the cardiac electrophysiology laboratory with a heart rate approaching that seen at baseline (if in sinus rhythm at the start of the procedure) and in sinus rhythm. It is accepted that some patients will require DC cardioversion if atrial fibrillation occurring during the infusion protocol persists for greater than 10 minutes.

It is also anticipated that it may be difficult for participants to tell whether they are undergoing a part of the study protocol or a part of their NHS ablation procedure at any particular time once they have entered the Cardiac Electrophysiology Laboratory. This is due to the use of sedation and the similarity between the participant experience in each part of the procedure. The potential for confusion will be clearly explained in the patient information sheet.

• Part B - Visit 3 – 6 week follow up

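### Exclusion after an infusion ends study involvement while that infusion's 24-hour death, stroke and MI window is still open, and the protocol does not reconcile the two

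*Protocol*

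**What the plan says.** Under Safety Endpoints associated with each infusion administration, the protocol lists "Death within 24 hours of start of study drug infusion protocol", the same for stroke, and "Myocardial Infarction within 24 hours of start of study drug infusion protocol". No exception is made for participants who are later excluded.

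Reasons for Discontinuation of Subject's Participation in Study gives two routes out that matter here.

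- Triggered by the infusion: "Subjects will also be excluded from continuation in the study if they develop anaphylaxis, chest pain or ECG features of myocardial ischaemia during the infusion".
- Loss of eligibility after enrolment, with the protocol's own example: "participant in SVT block has electrophysiology study that demonstrates atrial tachycardia rather than ANRT or AVNRT".

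End of Study Actions then puts exclusion on the same footing as finishing the schedule: "been excluded from continued participation or having completed their final visit or ambulatory ECG recording, participants will have completed their involvement in the study". Excluded participants are replaced, and data gathered up to withdrawal are permitted, not required, in the results. Afterwards the only link is that participants are told they may contact the team.

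**The concern.** Stopping the study drug and leaving follow-up are different acts, and the protocol treats them as one. The participants removed by the first route have just shown the warning signs of the harm discussed under Administration of Isoprenaline: raised myocardial oxygen demand, ischaemia and possible infarction. If their involvement ends there, the 24-hour endpoints have no planned means of ascertainment in the people for whom they matter most. A low or zero event count would then be hard to interpret. No analysis plan can recover information that the protocol has stopped collecting.

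**Working it through.** No sample size or power figure bears on this point, so there is no stated figure to reproduce. The check compares sections, then does two short calculations.

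**1. Time left in the safety window.** Infusion Protocol gives five steps of 2 minutes and a 10-minute washout: 5 × 2 + 10 = 20 minutes at most. An exclusion triggered during it leaves at least 24 h − 20 min = 23 h 40 min. If the 30 minutes of monitoring required for all subjects are still completed after the end of the protocol, 24 h − 50 min = 23 h 10 min remain. No study contact is planned in that time.

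**2. Loss of eligibility in Part B.** Part B, Visit 2 places sedation and the pre-ablation infusion ahead of the electrophysiology study: "Before catheters are inserted into the heart, the patient will be sedated so that they are asleep but responsive to voice", and the infusion follows. A participant reclassified by that study has therefore normally been infused the same day, and that window is open too. The exception is a participant in persistent arrhythmia when the infusion is due: "then that infusion will not be performed and the operator will proceed to the ablation procedure". Such a person may leave without having been infused.

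**3. Study contacts at which a 24-hour event would surface.**

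| Situation | If continuing | If excluded |
|---|---|---|
| Part A, after first infusion | Visit 3, at least 2 weeks later | none |
| Part A, after second infusion | none; participation ends with that visit | none |
| Part B | 6-week visit; 3-month visit with study interview | none as a study participant |

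Exclusion therefore removes a contact after the first Part A infusion and throughout Part B. It makes no difference after the second Part A infusion.

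**4. Whether the safety reporting rules fill the gap.** Active follow-up under Serious Adverse Events starts once a serious event has been reported. The serious-event definition requires an event to be unexpected as well as untoward, while Administration of Isoprenaline lists chest discomfort among the expected side effects. The chest-pain exclusion carries no severity threshold. A participant can thus be excluded for chest pain that never becomes a serious event report.

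**5. Informative loss against lost precision (illustration only).** Take 35 per arm, as in Experiments 3 and 4, and suppose no safety event is seen. The one-sided 95% upper limit U solves (1 − U)^n = 0.05, so U = 1 − 0.05^(1/n). With n = 35, U = 8.2%. The number m lost after infusion is not in the documents; 1, 2 and 5 are assumed.

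| m lost | n observed | U from those observed | Rate if all m had an event (m/35) |
|---|---|---|---|
| 1 | 34 | 8.4% | 2.9% |
| 2 | 33 | 8.7% | 5.7% |
| 5 | 30 | 9.5% | 14.3% |

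The upper limit barely moves, yet with 5 lost the extreme-case rate lies above it. The last column is a bound, not a prediction. It shows that the difficulty is who is lost, not how many.

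**The case against.** The case against is substantial, and much of it stands.

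- A reader might infer that the 24-hour endpoints formally stop at exclusion. The protocol never says so: they attach to each infusion without exception. The fault is an unreconciled conflict, not a stated cessation.
- No 24-hour contact is described for any participant, so ascertainment soon after release is passive for all. That is correct. A difference remains because most continuing participants return to the study and excluded ones do not.
- The safety rules are stronger than a quick reading suggests. Chest pain, angina and anaphylaxis are not on the list of reactions spared full reporting. All adverse events are to be reported, events that may jeopardise the participant should be considered serious, and a serious uncommon or rare event suspends the study. Cases judged serious would be followed. The gap is confined to milder chest pain or ischaemia.
- A reader might infer that reclassified participants are also at higher risk, or that losses fall almost wholly in the isoprenaline arm. Nothing links a changed diagnosis to higher risk. It can arise in both arms under 1:1 randomisation, and sometimes without an infusion.
- A reader might infer that no all-infused safety population exists. Recorded adverse events are to be analysed, and analysis sets are commonly defined in an analysis plan, which is not shown here. That is no finding.
- Later follow-up carries limited weight. Part A has no follow-up visits, and the 12-month outcomes are descriptive and come from the additional monitoring group.

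**Conclusion.** The point holds in a limited form. The discontinuation and end-of-study text ends involvement at exclusion. The endpoint text requires a 24-hour outcome for every infusion. Nothing says how the two fit together. For infusion-triggered exclusions, more than 23.5 hours of the window are open at that moment (more than 23 hours if the post-infusion monitoring is completed), and the later contacts that would reveal an event are lost, except after the second Part A infusion, where there are none. That loss is informative, because the reason for leaving is itself a sign of the harm being counted. For loss of eligibility it is not shown to be informative.

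The documents give no rate of chest pain, ischaemia or reclassification, so neither the number affected nor the share of events missed can be estimated. The conclusion rests on taking completed involvement at its plain meaning, and on some excluding events not being judged serious. The primary comparisons of atrial fibrillation are not at issue here. This is a cheap improvement to the safety endpoints.

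**What to change.** Amend Reasons for Discontinuation and End of Study Actions as follows.

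1. Exclusion after enrolment means no further study infusion, not the end of participation.
2. Anyone who received any part of a study infusion stays in for that infusion's 24-hour death, stroke and MI endpoints, with one status check at or after 24 hours, unless consent is withdrawn.
3. In Part B, safety information available at the usual-care 3-month review is also collected for them, on the same condition.
4. The 24-hour endpoints *will*, not *may*, be reported for all infused participants, including those excluded or replaced.

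The infusion-stopping and clinical exclusion rules stay as they are.

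The cost is protocol wording, one extra contact per excluded participant, and possibly a less favourable safety table. A check made only in excluded participants leaves ascertainment passive for the others, so the report should state how each group's 24-hour status was obtained.
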